Research question and objectives	
Research question
 
What is the prevalence of rare blood cancers in Europe?
 
Study objectives
 
Objective 1: To estimate the prevalence of follicular lymphoma between 1st January 2010 and the end of available data in data sources from across Europe, stratified by age and sex
 
Objective 2: To estimate the prevalence of diffuse Large B-Cell Lymphoma between 1st January 2010 and the end of available data in data sources from across Europe, stratified by age and sex
 
Objective 3: To estimate the prevalence of multiple myeloma between 1st January 2010 and the end of available data in data sources from across Europe, stratified by age and sex
 
Objective 4: To estimate the prevalence of chronic lymphocytic leukaemia between 1st January 2010 and the end of available data in data sources from across Europe, stratified by age and sex
 
Objective 5: To estimate the prevalence of acute myeloid leukaemia between 1st January 2010 and the end of available data in data sources from across Europe, stratified by age and sex and sex
 
Objective 6: To estimate the prevalence of acute lymphocytic leukaemia between 1st January 2010 and the end of available data in data sources from across Europe, stratified by age and sex

Country(-ies) of study	The Netherlands, Spain, United Kingdom, Belgium, and Germany

	D2.2.3 – Study Protocol for C1-001	
	Author(s): [name], [name], [name], [name]	Version: 2.0 - Final
		Dissemination level: Public

Authors	[name] ([contact]); [name] ([contact])
----------------	---

	D2.2.3 – Study Protocol for C1-001	
	Author(s): [name], [name], [name], [name]	Version: 2.0 - Final
		Dissemination level: Public

LIST OF ABBREVIATIONS

Acronyms/terms	Description
Point prevalence	Total number of individuals with an outcome of interest at a particular time divided by the population at risk of having the outcome at that time
Period prevalence	Total number of individuals with an outcome of interest during a particular period divided by the population at risk of having the outcome during the period
Complete prevalence	In complete prevalence outcome events are considered to persist indefinitely. That is, regardless of how long ago an individual had the event, the person remains as a prevalent case.
Partial prevalence	In partial prevalence outcome events are considered to persist for a fixed amount of time following an initial diagnosis. That is, to be a prevalent case at a given time, an individual must have had the outcome observed for the first time during a fixed time in the past (e.g. 5 years).

	D2.2.3 – Study Protocol for C1-001	
	Author(s): [name], [name], [name], [name]	Version: 2.0 - Final
	Dissemination level: Public	

1. TITLE

Prevalence of rare blood cancers in Europe

3. ABSTRACT

Title

Prevalence of rare blood cancers in Europe

Rationale and Background

Substantial uncertainty surrounds the prevalence of rare blood cancers. Using real-world data, brought together as part of DARWIN EU®, we aim to estimate the prevalence of rare blood cancers in order to see if they still meet the condition to be classified as a rare disease.

Research question and Objectives

Research question

What is the prevalence of rare blood cancers in Europe?

Study objectives

Objective 1: To estimate the prevalence of follicular lymphoma between 1st January 2010 and the end of available data in data sources from across Europe, stratified by age and sex

Objective 2: To estimate the prevalence of diffuse Large B-Cell Lymphoma between 1st January 2010 and the end of available data in data sources from across Europe, stratified by age and sex

Objective 3: To estimate the prevalence of multiple myeloma between 1st January 2010 and the end of available data in data sources from across Europe, stratified by age and sex

Objective 4: To estimate the prevalence of chronic lymphocytic leukaemia between 1st January 2010 and the end of available data in data sources from across Europe, stratified by age and sex

Objective 5: To estimate the prevalence of acute myeloid leukaemia between 1st January 2010 and the end of available data in data sources from across Europe, stratified by age and sex

Objective 6: To estimate the prevalence of acute lymphocytic leukaemia between 1st January 2010 and the end of available data in data sources from across Europe, stratified by age and sex

	D2.2.3 – Study Protocol for C1-001	
	Author(s): [name], [name], [name], [name]	Version: 2.0 - Final
		Dissemination level: Public

Research Methods

Study design

Population-based cohort

Population

All people in a database will be eligible for inclusion in the study. Included study participants will need to have some observation time during the study period and, for the primary analysis, have a year of prior history available. In sensitivity analyses the requirement for prior history will first be removed, and then increased to three years.

Variables

Two age groupings will be used in the study: 1) 0-9; 10-19; 20-29; 30-39; 40-49; 50-59; 60-69; 70-79; 80-89; 90-99; 100+, and 2) 0-44; 45-64; 65 and over. The sex (male/ female) of study participants will also be identified.

Study outcomes will be identified based on the presence of a relevant diagnosis or observation. For the primary analysis, 5-year partial prevalence will be estimated and so individuals will be considered as a prevalent case if they have had their first diagnosis in the prior 5 years. In sensitivity analyses, 2-year partial prevalence and complete prevalence will be estimated. For the latter, once identified as a case, an individual will remain so until their exit from the study (i.e. considering people diagnosed with malignancies to always be affected by the condition).

Data sources

1. Integrated Primary Care Information Project (IPCI), The Netherlands
2. Sistema d'Informació per al Desenvolupament de la Investigació en Atenció Primària (SIDIAP), Spain
3. The Clinical Practice Research Datalink (CPRD) GOLD database
4. IQVIA LPD Belgium
5. IQVIA DA Germany

Sample size

No sample size has been calculated as this is a Disease Epidemiology Study where we are interested in the prevalence of haematological cancers in as large and representative a denominator population as possible.

Data analyses

In line with EMA guidelines for the estimation of the prevalence of rare disease, point prevalence will be used for the primary analysis. The prevalence of each outcome of interest calculated on an annual basis as of the 1st January for each year, estimated overall and stratified by age and sex. As a sensitivity analysis annual period prevalence will also be estimated. A minimum cell count of 5 will be used when reporting results, with any smaller counts obscured.

	D2.2.3 – Study Protocol for C1-001	
	Author(s): [name], [name], [name], [name]	Version: 2.0 - Final
		Dissemination level: Public

4. AMENDMENTS AND UPDATES

Number	Date	Section of study protocol	Amendment or update	Reason
2.0	03/11/2022	All	Update	Updated following EMA assessment.

	D2.2.3 – Study Protocol for C1-001	
	Author(s): [name], [name], [name], [name]	Version: 2.0 - Final
		Dissemination level: Public

5. MILESTONES

STUDY SPECIFIC DELIVERABLE	TIMELINE
Draft Study Protocol	1 st September 2022
Final Study Protocol	1 st November 2022
Creation of Analytical code	To be confirmed
Execution of Analytical Code on the data	To be confirmed
Interim Study Report (if applicable)	To be confirmed
Draft Study Report	To be confirmed
Final Study Report	To be confirmed

6. RATIONALE AND BACKGROUND

The Committee for Orphan Medicinal Products (COMP) is the European Medicines Agency's (EMA) committee responsible for recommending orphan designation of medicines for rare diseases. It was established in 2000 when new legislation was introduced to encourage the development of medicinal products for rare diseases. One important criterion for granting an orphan designation to a medicine is a prevalence threshold of maximum 5 in 10,000 for the associated condition at the time of application. Of the submissions to the COMP, around 35% are for oncological conditions and around 42% of designations of orphan medicinal products in oncology granted by the COMP between 2000 and 2015 related to rare haematological malignancies.¹

Prevalence estimates, such as of rare haematological malignancies, are a frequent source of uncertainty when submissions to the COMP are being assessed.² In particular, limited availability of population-based epidemiological studies has often led to the use of indirect methods for calculations of prevalence which often involves various assumptions. In addition, time trends in prevalence may also be present meaning that certain conditions that previously satisfied the prevalence criterion for orphan designation in the past may no longer do so. Indeed, increased prevalence has previously been noted for a number of rare haematological malignancies, which may be explained by improved survival and aging populations.¹ In this study the prevalence of rare blood cancers will be measured in Europe over time.

	D2.2.3 – Study Protocol for C1-001	
	Author(s): [name], [name], [name], [name]	Version: 2.0 - Final
	Dissemination level: Public	

7. RESEARCH QUESTION AND OBJECTIVES

What is the prevalence of rare blood cancers in Europe?

Study objectives

Objective 1: To estimate the prevalence of follicular lymphoma between 1st January 2010 and the end of available data in data sources from across Europe, stratified by age and sex

Objective 2: To estimate the prevalence of diffuse Large B-Cell Lymphoma between 1st January 2010 and the end of available data in data sources from across Europe, stratified by age and sex

Objective 3: To estimate the prevalence of multiple myeloma between 1st January 2010 and the end of available data in data sources from across Europe, stratified by age and sex

Objective 4: To estimate the prevalence of chronic lymphocytic leukaemia between 1st January 2010 and the end of available data in data sources from across Europe, stratified by age and sex

Objective 5: To estimate the prevalence of acute myeloid leukaemia between 1st January 2010 and the end of available data in data sources from across Europe, stratified by age and sex

Objective 6: To estimate the prevalence of acute lymphocytic leukaemia between 1st January 2010 and the end of available data in data sources from across Europe, stratified by age and sex

Table 1. Primary research questions and objectives

Objective:	To estimate the prevalence of rare blood cancers (follicular lymphoma, diffuse Large B-Cell Lymphoma, Multiple Myeloma, Chronic Lymphocytic Leukaemia, Acute Myeloid Leukaemia, Acute Lymphocytic Leukaemia)
Hypothesis:	Not applicable
Population (mention key inclusion-exclusion criteria):	All persons in the selected databases will be eligible for inclusion in the study (for main analysis all patients need to have at least 1 year of database history)
Exposure:	Not applicable
Comparator:	Not applicable
Outcome:	Rare blood cancers: Follicular lymphoma, Diffuse Large B-Cell Lymphoma, Multiple Myeloma, Chronic Lymphocytic Leukaemia, Acute Myeloid Leukaemia, Acute Lymphocytic Leukaemia
Time (when follow up begins and ends):	1 st January 2010 – end of available data within data sources
Setting:	5 Electronic Health Care Record databases across Europe
Main measure of effect:	Prevalence

	D2.2.3 – Study Protocol for C1-001	
	Author(s): [name], [name], [name], [name]	Version: 2.0 - Final
		Dissemination level: Public

8. RESEARCH METHODS

8.1 Study type and Study Design

Population-level descriptive epidemiology within a cohort study. Study design diagrams with description of follow-up are described below. The study will include all people in a database and, for the primary analysis, have a year of prior history available. The prevalence of each outcome of interest calculated on an annual basis as of the 1st January for each year, estimated overall and stratified by age and sex. As a sensitivity analysis annual period prevalence will also be estimated. 5-year partial prevalence will be used for the primary analysis, with individuals will be considered as a prevalent case if they have had their first diagnosis in the prior 5 years. In sensitivity analyses, 2-year partial prevalence and complete prevalence will be estimated. For the latter, once identified as a case, an individual will remain so until their exit from the study.

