8.6.2. Outcome/s (where relevant)

Outcome cohort definitions for partial and complete prevalence

Complete prevalence represents the number of persons alive at the specific point in time regardless of how long ago the diagnosis was, while partial prevalence limits the number of patients to those diagnosed during a fixed time in the past.⁶ To operationalise this definition outcome cohorts will be defined which vary in how the cohort exit is defined. For complete prevalence an individual will remain in the outcome cohort until the end of their observed time at risk. Meanwhile, for partial prevalence, an individual will exit the outcome cohort after a certain number of days has elapsed since the first record indicating them to be a prevalent case (e.g. 1,825 days for 5-year partial prevalence).

Follicular lymphoma

Follicular lymphomas are the second leading Non-Hodgkin’s lymphomas and can be diagnosed accurately on morphologic findings alone: B-cell in follicular centre. Many patients are diagnosed incidentally or at a time when their lymphoma is not causing symptoms or signs of organ function impairment. The major differential diagnosis is between lymphoma and reactive follicular hyperplasia. The coexistence of diffuse large B-cell lymphoma must be considered. Patients with follicular lymphomas are often subclassified, or graded, into those with predominantly small cells, those with a mixture of small and large cells, and those with predominantly large cells. The typical natural history is a pattern of continuous relapses with a diminishing sensitivity to chemotherapy. On average, most patients will live with follicular lymphoma for 15 to 20 years.

For this study, cases will be identified based on a record indicating a diagnosis or observation of follicular lymphoma. A clinical description along with a preliminary code list is provided in Appendix 1. For the primary analysis, 5-year partial prevalence will be estimated and so individuals will be considered as a prevalent case if they had a relevant record observed in the prior 1,825 days. In sensitivity analyses, 2-year partial prevalence

	D2.2.3 – Study Protocol for C1-001	
	Author(s): [name], [name], [name], [name]	Version: 2.0 - Final
		Dissemination level: Public

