	Author(s): [name], [name], [name], [name]	Version: 2.0 - Final
		Dissemination level: Public

Plan

- observation
Reasonable alternative. Numerous studies have shown that treating patients with asymptomatic disease does not improve survival compared with a program of close observation with treatment reserved for symptomatic disease progression or organ dysfunction
- radiotherapy
Although FL is highly sensitive to chemotherapy and radiotherapy, these therapies are usually not ultimately curative, except in the setting of early-stage disease.
- chemotherapy associated with rituximab (R-CHOP, R-Bendamustine) - Monoclonal antibody against CD20, [rituximab], alone or its use in combination with chemotherapy. Treatment decisions are often determined by the indication for treatment and/or by the volume of disease being treated. For patients requiring therapy for inflammatory or autoimmune phenomenon thought to be driven by FL, or for patients with low volume disease, single-agent [rituximab] For patients with a larger volume of disease at the time of treatment initiation, the addition of chemotherapy (CHOP, R-CHOP, R-CVP). [cyclophosphamide], [doxorubicin], [vincristine] and [prednisone], improved survival in this disease. The combination of [bendamustine], [rituximab] [R-CHOP] longer response duration and less toxicity.
BR then has become the standard of care for the first-line therapy of medium to high-volume FL. Similarly, the addition of maintenance [rituximab] improves response duration when used in newly treated FL patients.
- Autologous and allogeneic hematopoietic stem cell transplantation yield high complete response -
- Targeted oral therapies like [lenalidomide] and the PI3 kinase inhibitor [idelalisib]

Prognosis

The typical natural history is a pattern of continuous relapses with a diminishing sensitivity to chemotherapy. On average, most patients will live with FL for 15–20 years.

May return spontaneously but partially and temporarily.

Can transform into a High-grade lymphoma (more aggressive) with poor prognosis in 20% of patients, (~3% per year). rapid growth of lymph nodes and the development of systemic B-symptoms. They have sometimes been described spontaneous remissions.

Prognostic scale: <https://www.mdcalc.com/calc/2320/follicular-lymphoma-international-prognostic-index-flipi>

	D2.2.3 – Study Protocol for C1-001	
	Author(s): [name], [name], [name], [name]	Version: 2.0 - Final

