Multiple myeloma (MM) is a malignant uncontrolled proliferation of plasma cells derived from one single clone. MM can affect many organs, typically bones and calcium metabolism (e.g. fractures or bone pain, hypercalcemia), kidneys (renal failure/ckd/aki), immune system (e.g. infection), blood (anemia, clotting), and more rarely neurologic.

The etiology of MM is unknown, and it is one of the most common blood cancers, with an estimated incidence rate ranging from 6 to 14/100,000, more common in ages 60-70+ and in ethnic minorities.

Presentation

Bone pain, fractures, and hypercalcemia are the most common manifestations of MM. Radiology would show (on top of fracture/pathologic fracture where present) lytic/osteolytic lesions in plain x-ray or ct scan. Bone lysis results in hypercalcemia, and related complications. Other typical features that lead to diagnosis include renal failure (ckd or aki) or bacterial infections like pneumonia or pyelonephritis. Recurrent infections are common. Bloods and urine labs are typically used to investigate/diagnose MM, and will show hypogammaglobulinemia, bence-jones proteins, hypercalcemia, and other alterations of proteinogram.

Assessment

Assessment will typically include imaging e.g. x-ray, ct scan, and sometimes bone gammagraphy or similar techniques. Also, bloods and urine are included often during investigation/diagnosis, typically including full blood counts, biochemistry, immunology, proteinogram, serum electrophoresis, β 2Microglobulin, LDH and serum albumin, and bence jones proteins

Diagnosis is typically obtained after bone marrow biopsy, where plasma cells monoclonal kappa or lambda light chains will be present. The most important differential diagnosis is MGUS (monoclonal gammopathy of unknown significance) or 'smoldering multiple myeloma'. These are far more common than MM, and sometimes preclude or transition to MM proper. It is estimated that about 1% of patients with MGUS transition every year to MM. Patients with MGUS would not have a bone marrow biopsy, but they will/should have repeat bloods over time to monitor/rule out MM.

Diagnostic Criteria

Monoclonal Gammopathy of Undetermined Significance (MGUS)

- Serum monoclonal protein (non-IgM type) <30 g/L
- Clonal bone marrow plasma cells <10%
- Absence of myeloma-defining events or amyloidosis that can be attributed to the plasma cell proliferative disorder

Smoldering	Multiple	Myeloma	(Asymptomatic	Myeloma)
Both	criteria	must	be	met:

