-Serum monoclonal protein (IgG or IgA) \geq 30 g/L or urinary monoclonal protein \geq 500 mg per 24 h and/or				
clonal bone marrow plasma cells				10–60%
-Absence of myeloma-defining events or amyloidosis				

	D2.2.3 – Study Protocol for C1-001	
	Author(s): [name], [name], [name], [name]	Version: 2.0 - Final
	Dissemination level: Public	

Symptomatic Multiple Myeloma
 Clonal bone marrow plasma cells or biopsy-proven bony or extramedullary plasmacytoma and any one or more of the following myeloma-defining events:
 Evidence of one or more indicators of end-organ damage that can be attributed to the underlying plasma cell proliferative disorder, specifically:

- Hypercalcemia: serum calcium >0.25 mmol/L (>1 mg/dL) higher than the upper limit of normal or >2.75 mmol/L (>11 mg/dL)
- Renal insufficiency: creatinine clearance <40 mL/min or serum creatinine >177 µmol/L (>2 mg/dL)
- Anemia: hemoglobin value of >20 g/L below the lower limit of normal, or a hemoglobin value <100 g/L
- Bone lesions: one or more osteolytic lesions on skeletal radiography, CT, or PET-CTc
- Any one or more of the following biomarkers of malignancy: i. Clonal bone marrow plasma cell percentagea ≥60%; ii. Involved: uninvolved serum free light chain ratio d ≥100; and/or iii. >1 focal lesion on MRI studies

Plan

Common treatments for MM include:

- Immunomodulatory drugs (IMiD) like Thalidomide, Lenalidomide, Pomalidomide
- Proteasome inhibitors (PI) like Bortezomib, Carfilzomib, Ixazomib
- Antibodies/monoclonal antibodies like Daratumumab, Elotuzumab, Isatuximab, Belantamab mafodotin
- Selective inhibitors of nuclear export (SINE) like Selinexor
- Histone deacetylase inhibitors like Panobinostat
- Alkylating agents like Melphalan, Cyclophosphamide, Bendamustine, Melflufen
- Cellular therapy like Idecabtagene vicleucel
- Glucocorticoids like Dexamethasone or Prednisone

Prognosis

Medial survival ranges from 30 to 60 months, with some advanced diagnoses surviving for no more than 6 months

Strengtheners

any of the treatments mentioned above, use of imaging and specific bloods also mentioned above

Preliminary code list

Condition domain

concept_id	concept_name
437233	Multiple myeloma
37016161	Light chain nephropathy due to multiple myeloma
37209514	Hypogammaglobulinemia due to multiple myeloma
4043713	Neuropathy due to multiple myeloma
4224628	Amyloid light chain amyloidosis due to multiple myeloma
4258135	Asymptomatic multiple myeloma

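### The primary 5-year partial prevalence leaves out most living follicular lymphoma patients and a sizeable share of myeloma patients, so it is biased downward for a check against 5 per 10,000

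*Protocol*

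**What the plan says.** The abstract gives the purpose: prevalence is estimated "in order to see if they still meet the condition to be classified as a rare disease". Section 6 gives the yardstick, "a prevalence threshold of maximum 5 in 10,000", and names improved survival as one reason why prevalence may have risen.

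For all six cancers alike, section 8.1 states that "5-year partial prevalence will be used for the primary analysis" and that "individuals will be considered as a prevalent case if they have had their first diagnosis in the prior 5 years". The opening of section 8.6.2 and section 8.8 put this into operation: the person leaves the outcome cohort a fixed number of days after the first record, 1,825 for the primary measure. Complete prevalence is planned for every cancer (Table 5, analyses 18 to 26), but only as sensitivity analysis.

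On survival, section 8.6.2 says: "On average, most patients will live with follicular lymphoma for 15 to 20 years". Appendix I says of chemotherapy and radiotherapy for this lymphoma that "these therapies are usually not ultimately curative", with an exception for early-stage disease. For multiple myeloma Appendix I describes a cancer "with an estimated incidence rate ranging from 6 to 14/100,000" and adds "Medial survival ranges from 30 to 60 months" (read here as median). Chronic lymphocytic leukaemia is described as of low aggressiveness, without a survival figure.

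Section 11 concedes that the 2-year and 5-year durations are arbitrary. The only direction of error it names for the duration choice is that complete prevalence may include people who have recovered.

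**The concern.** The question is how many people are living with each cancer, compared with a fixed limit. A window that drops living patients after five years can only lower that number, and lowers it most where survival is long. The error therefore runs in one direction, towards remaining under the limit. Survival gained after year five, which is part of the reason section 6 gives for repeating the exercise, does not move the primary estimate.

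The abstract's appeal to EMA guidelines supports point prevalence rather than period prevalence. It does not support the 5-year window. The protocol states no reason for applying one window to cancers with such different courses, and does not warn that the primary measure undercounts long survivors.

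**Working it through.** The protocol states no expected prevalence, so there is no planned figure to reproduce. The check uses a steady-state model. Constant incidence, a stable population and the survival shape are assumptions.

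**Formulas.** With annual incidence I and survival S(t) from diagnosis:
- Complete prevalence = I × ∫S(t)dt from 0 to infinity = I × mean survival.
- 5-year partial prevalence = I × ∫S(t)dt from 0 to 5.
- Share of living patients omitted = 1 − partial/complete.

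**Upper bound.** Since S(t) ≤ 1, partial ≤ 5 × I. At I = 10 per 100,000 per year this is 50 per 100,000 = 5 per 10,000. At or below that incidence the primary measure cannot exceed the limit, whatever the survival.

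**Follicular lymphoma** (15 and 20 years, section 8.6.2), share omitted:
- Fixed duration: (15−5)/15 = 67%; (20−5)/20 = 75%.
- Exponential, figure read as mean: exp(−5/15) = 72%; exp(−5/20) = 78%.
- Exponential, figure read as median: 2^(−5/15) = 79%; 2^(−5/20) = 84%.
- Weibull, figure read as median, shape 1.5: 73% and 79%; shape 0.8: 84% and 88%.

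A true 5 per 10,000 would be reported as 5 × (1 − 0.67) ≈ 1.7 at best, and as 5 × (1 − 0.84) ≈ 0.8 with the exponential median of 20 years. The protocol gives no incidence for this lymphoma, so only the ratio can be shown.

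**Multiple myeloma** (6 to 14 per 100,000, read as per year; median 30 to 60 months; Appendix I). With exponential survival, mean = median/ln 2 and share omitted = 2^(−5/median): 25% at 30 months, 40% at 45, 50% at 60. With Weibull shape 1.5 the range from 30 to 60 months is 7% to 33%; with shape 0.8 it is 40% to 61%.

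Prevalence per 10,000, exponential survival (45 months and 10 per 100,000 are midpoints chosen for this check):

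| Incidence per 100,000 | Median (months) | Complete | 5-year partial |
|---|---|---|---|
| 6 | 30 | 2.2 | 1.6 |
| 6 | 60 | 4.3 | 2.2 |
| 10 | 30 | 3.6 | 2.7 |
| 10 | 45 | 5.4 | 3.3 |
| 10 | 60 | 7.2 | 3.6 |
| 14 | 30 | 5.05 | 3.8 |
| 14 | 60 | 10.1 | 5.05 |

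Example for 10 per 100,000 and 60 months: mean = 5/0.693 = 7.21 years; complete = 10 × 7.21 = 72.1 per 100,000 = 7.2 per 10,000; partial = 7.2 × (1 − 0.5) = 3.6.

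Incidence at which each measure passes 5 per 10,000 (exponential): at 60 months, complete 6.9 and partial 13.9 per 100,000; at 45 months, 9.2 and 15.3; at 30 months, 13.9 and 18.5.

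**Dependence on survival shape.**
- 10 per 100,000 and 60 months: complete is 9.0 (shape 0.8), 7.2 (exponential) and 5.8 (shape 1.5); partial is 3.5, 3.6 and 3.9. The reversal holds in all three.
- 10 per 100,000 and 45 months: complete is 6.7 (shape 0.8), 5.4 (exponential), 4.8 (shape 1.2) and 4.3 (shape 1.5). The reversal disappears for the last two.
- 30 months, exponential: a reversal occurs only at about 13.9 to 14 per 100,000. With shape 0.8 and 14 per 100,000, complete would be 14 × 4.48/10 = 6.3.

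**The case against.** The strongest reply is that nothing is hidden. Complete prevalence is pre-specified for every cancer, Table 1 says no hypothesis applies, no rule compares a result with 5 per 10,000, and results are shown by database. All of this stands. A reader might infer that the plan will declare a cancer rare on the 5-year figure; the document contains no such rule. What remains is that the estimate labelled primary fits the stated aim poorly, and nothing says how to read the two measures when they disagree.

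Second, the 1,825 days run from the first record, not from true diagnosis. Belgian and German observation time starts at the first consultation, and the myeloma code list includes relapse, remission and history codes, so some long survivors will enter late and be counted. The undercount in a given database may thus be smaller than calculated. The cancer-specific paragraphs of section 8.6.2 also define a case by a relevant record in the window rather than a first one, which would keep relapsing patients. Section 8.1, section 8.8, the 5-year footnote to Table 5 and the exit rule all point to the first diagnosis or record, and the calculation follows them.

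Third, complete prevalence has its own faults. It may include cured people, and look-back limits it: SIDIAP starts in 2006, Belgium in 2005, and IPCI has a median follow-up of 2.6 years, although IPCI keeps earlier data as history. If look-back ends at database start, complete and 5-year prevalence nearly coincide in 2010 in SIDIAP and Belgium and then drift apart, which could look like a rising trend. This stands, and it argues for adding the measure with limits on its reading rather than substituting it.

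**Conclusion.** The concern holds as a downward bias in the measure labelled primary. It is firm for follicular lymphoma: two thirds to three quarters or more of living patients are omitted under every survival shape tried, counting from true diagnosis. For myeloma the omitted share is 25% to 50% under exponential survival and depends on shape. The bound at 10 per 100,000 per year does not depend on survival shape, but does assume a steady state and correctly dated diagnoses.

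Several stronger readings are not supported:
- That myeloma prevalence is shown to exceed the limit. A reversal is possible within the stated ranges, but uncertain at 45 months and essentially absent at 30 under exponential survival. At 14 per 100,000 and 60 months both measures exceed 5, so that case is no reversal.
- That follicular lymphoma or chronic lymphocytic leukaemia exceeds the limit. The first has no incidence in the protocol and the second no survival figure, so the argument for the latter is qualitative.
- That these cancers are all described as incurable. The text says only that follicular lymphoma therapy is usually not curative, with an early-stage exception.
- That improved survival cannot show in the primary result. Gains within the first five years do raise it, which matters for myeloma.

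**What to change.** 1. Make complete point prevalence with 365 days of prior history (Table 5, analysis 18) co-primary with analysis 1 for follicular lymphoma and multiple myeloma, and for chronic lymphocytic leukaemia on qualitative grounds. Leave analysis 1 as it is for the other three cancers.
2. State that, for these three cancers, analysis 1 alone cannot support a conclusion of under 5 per 10,000.
3. State how analysis 18 is to be read: mainly in the latest years and in databases with long look-back. A value under 5 is inconclusive where look-back is short. It is not to be used for time trends in databases that start in 2005 or 2006.
4. Add to section 11 that partial prevalence undercounts people living beyond the window, most of all in cancers with long survival.
5. Reconcile first diagnosis with relevant record across sections 8.1, 8.6.2, 8.8 and the Table 5 footnotes.

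The cost is relabelling and a few sentences, since the analysis is already planned. The downside is a second headline figure that may include cured people and is limited by look-back.
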